*Current pharmacological treatments for smoking cessation:* Current first line treatments for smoking cessation include NRT (including nicotine gum, lozenge, inhaler and spray), bupropion, and varenicline (10, 18). With some minor differences, these treatments increase the odds of quitting smoking by 2 to 3 fold (19, 20). Still, this only translates to smoking abstinence at one year for 10%-30% of smokers who attempt to quit. Combination treatments may be more effective than a single agent for smoking cessation suggesting that there is room for improved efficacy among smoking cessation treatments(21). Unfortunately, concerns about the neuropsychiatric adverse effects of varenicline and bupropion, especially suicidal ideation and behavioral changes, limit their use alone or in combination with other medications (22). Among NRTs, there are no significant differences between different products in their efficacy for smoking cessation (23). Transdermal nicotine patch (TNP) has advantages over other NRTs for its consistent delivery of nicotine for 24 hours, ease of use and favorable adverse effect profile.

*Role of sex hormones in addictive behaviors:* Both estradiol and progesterone have well-documented actions on multiple neurotransmitters affecting the brain reward pathway (24). While estradiol activates the reward pathway, progesterone has the opposite effects (25). For example, in the mid-follicular phase of the human menstrual cycle (when progesterone is low and estrogen is high), as compared to the progesterone dominant luteal phase, the reward circuitry (midbrain, striatum, and left fronto-polar cortex) is more highly activated (26). As summarized below, the therapeutic potential of sex hormones, especially progesterone, suggest that progesterone may have a role in treatment of nicotine addiction in female smokers (27).

*Progesterone as a neurosteroid:* Progesterone is a hormone produced by male and female gonads, adrenal glands and in the brain by oligodendrocytes and neurons (hence the moniker "neurosteroid") (28). In premenopausal women, progesterone levels are low in the follicular phase of the menstrual cycle, and are comparable to those in men, < 1 ng/ml (29). Women have higher progesterone levels than men during the luteal phase of the menstrual cycle (2-28

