#### *Human subjects*

**Recruitment:** Recruitment will take place over 1.5 years, requiring enrollment of approximately 2-3 subjects per month. In our previous studies, we have been able to recruit on average 4 female smokers per month. Recruitment is further explained in Human Subjects but will be accomplished by direct screening in our reproductive health centers (20% of women seen for services in these centers are smokers), direct mail invitations, posters and flyers placed in local obstetrician-gynecologist offices. We have successfully used these techniques to recruit substance users, smokers and women with premenstrual dysphoric disorder in prior clinical trials. [name] has a secondary appointment in Obstetrics & Gynecology and has conducted numerous studies that entailed screening women in the reproductive health settings of Yale New Haven Hospital and their faculty (see Biosketch).

Update June 2017: All participants had blood levels of progesterone drawn. We were blind to assignment of participants but at the end of the study found that those who were randomized to active progesterone had low progesterone levels. This could be due to the progesterone preparation or the fact that smokers metabolize it very quickly. In any case, the low progesterone levels in the active treatment group obviates our ability to test our hypothesis that progesterone augmentation assists abstinence for smokers. Given the lack of funds, we cannot repeat the project. Rather, we are recruiting a second cohort and are using a commercially available oral micronized progesterone rather than the previous medication that was compounded for the study. We plan to enroll a minimum of 12 people with an imbalanced ratio of 6 active to 1 placebo. We will continue to obtain plasma levels of progesterone. This will enhance our ability to test our hypothesis. If need be in a final analysis, and give that this is a pilot project, we may be able to use the participants randomized to placebo in the first cohort and second cohort and the participants randomized to active in the second cohort.

Update September 2017: We request an additional blood draw (timeline is around Visit #6 or #7 to confirm progesterone plasma levels and compliance with pill taking. The second blood draw will be the same as the first one, completed at a professional lab on the first floor of the research site building. Approximately 6 ccs of blood will be drawn for each.

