provided for the quit attempt. Assessments will be repeated although the neurocognitive battery will only be done a second time at this first follow up visit. A blood draw will be completed twice throughout the study, the first around Visit #2 and the other around Visit #6 or Visit #7 at a professional lab on the first floor of the research site building. Approximately 6 ccs of blood will be drawn for each.

Other assessments will be conducted weekly for the additional weeks of the study. Assessments will include a weekly calendar of cigarettes smoked, if any, breath CO. We will collect urine for cotinine if the breath test is negative and there are concerns about compliance with TNP. If there is a possibility that a participant is pregnant (i.e. she is not menstruating or in the week following menstruation) we will also test urine for positive pregnancy. Additionally, subjects will have brief behavioral treatment sessions for smoking abstinence.

End of study (Visit 8), Termination and follow-up: At the end of the 8-week treatment period, participants will complete their weekly ratings, collect breath CO. Participants and study staff will be asked to guess their treatment condition (progesterone or placebo) and will discontinue study capsules and TNP. All participants will be encouraged to remain abstinent from smoking (9). Follow-up visits will be scheduled at 1 and 3 months after the end of the study. At follow up, assessments of smoking and the PANAS will be repeated. We will not repeat the neurocognitive measures.

Strategies to minimize attrition and enhance follow up: We will: 1) rapidly assign study treatments after application confirmation of eligibility, 2) thoroughly explain study treatments and requirements, and 3) specify uniform procedures across treatment conditions regarding study staff's handling of participants who miss or come late to sessions. Study investigators will monitor participants who drop out and explore with the staff reasons for the dropouts. We will follow the full randomized sample, regardless of their retention in treatment, by including: 1) a thorough explanation at the consent interview of the importance of follow-ups, 2) collecting at least three verified locators who are likely to have knowledge of a subject's whereabouts, 3) paying participants to cover transportation and parking for follow-up visits.

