#### *Treatment Conditions*

Transdermal Nicotine Patch (TNP): TNP has been studied extensively as a smoking cessation treatment. Meta-analyses find that there is little difference among the types of NRTs although the patch provides a constant and slow delivery of nicotine. (17) The 24-hour delivery system is available in 7-, 14-, or 21-mg doses. Smokers who smoke more than 10 cigarettes/day begin with a 21-mg/d nicotine patch for the first 4 weeks and switch to 14 mg/d on weeks 5 and 6, and to 7 mg/d on weeks 7 and 8. Smokers who smoke between 5-10 cigarettes/day begin with a 14-mg/d nicotine patch for the first 6 weeks and switch to 7 mg/d on weeks 7 and 8. TNP is generally well-tolerated and has few side effects (skin irritation, nausea, vomiting, sweating, mood and sleep disturbances). In addition, once-daily dosing may lead to better compliance. Neither longer term (> 8 weeks) nor a higher dose (> 21 mg/d) of nicotine patch improves efficacy over the standard treatment (17).

Progesterone: The recommended dose of progesterone for hormone replacement treatment is 200 to 400 mg/day. We chose the 200 mgs BID because at this dose progesterone improved cognitive performance (6) but was associated with lower craving scores. After oral administration, micronized progesterone reaches its peak plasma levels in two to three hours and has an elimination half-life of three to four hours (18). Because of the short half-life of micronized progesterone, progesterone will be given twice daily to maintain stable plasma level of progesterone.

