pattern mixture models (26) and perform sensitivity analyses. In sensitivity analyses, participants who miss visits will be coded as smoking. Exploratory analysis will include plasma estradiol and progesterone levels as covariates in order to determine if they contribute to treatment response and PANAS scores as mediators of response to progesterone or placebo. Secondary analyses (the MNWS QSU-B) will be modelled similarly. The main outcome measures for the Stroop test are throughput and interference score. For the SST, the main outcomes are stop signal reaction time (msec) and go reaction time (msec). We will use hierarchical linear models with each cognitive measure as separate longitudinal outcomes and treatment group assignment as regressors.

**Power:** The sample size of 25 per condition was selected to provide an adequate assessment of feasibility and estimate effect sizes. Nonetheless, we determined what level of power we would have based upon a significance level of  $p < 0.05$ , 2 sided test for 7-day or prolonged abstinence. If rates of abstinence are 0.2 in the TNP only group and 0.4 in the progesterone and TNP group then the power would be 88%. If the rate of abstinence in the treated group is 0.38, power is reduced to 80%. In prior studies with the Stroop and SST, we found effect sizes  $> 0.5$  of progesterone vs placebo. Our sample size would have adequate power ( $> 80\%$ ) to detect a 2-fold difference in response. Clearly, these are large differences between groups but would provide a stable effect size estimate for a larger trial if findings are suggestive of a therapeutic effect of the combination treatment.

**Timeline:** We will use the first 3 months for study set up that will include final human subjects' approval, hiring and training of staff, database set up, computerization of the interview and assessment measures. Recruitment will begin immediately afterward. We will conduct ongoing data cleaning and will prepare reports for the human subjects' board, the DSMB and NCI at regular intervals. The final analysis and study report will occur in the last 3 months of the work period.

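### Progesterone draws are not tied to the last capsule, nor the second draw to cycle phase, so a low level at either draw or a raised level at the second cannot be read as the plan intends

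*Combined protocol and SAP*

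**What the plan says.** Section V, Study Procedures (Treatment Phase) places the two draws "the first around Visit #2 and the other around Visit #6 or Visit #7". The September 2017 update under Human subjects, which requests the second draw, gives its purpose as "to confirm progesterone plasma levels and compliance with pill taking". Visit 2 itself is placed around cycle days 7-11, and later visits are weekly. Pill count is named separately as the compliance measure.

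Treatment Conditions says that oral micronized progesterone reaches "peak plasma levels in two to three hours and has an elimination half-life of three to four hours", and is given twice daily for that reason. The Background (Progesterone as a neurosteroid) says "progesterone levels are low in the follicular phase of the menstrual cycle", at under 1 ng/ml, against 2-28 ng/ml in the luteal phase.

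The levels have already carried weight. The June 2017 update states that "low progesterone levels in the active treatment group obviates our ability to test our hypothesis". It changes the preparation, opens a second cohort of at least 12 women at 6:1, and allows for a final analysis that leaves out the first cohort's active arm. The Data Analysis text under Statistical Considerations adds: "Exploratory analysis will include plasma estradiol and progesterone levels as covariates".

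**The concern.** A drug with a half-life of a few hours gives a plasma level that depends heavily on when blood is taken. The documents shown set no interval between capsule and draw and do not ask for the time of the last dose. A low level may therefore be a trough in a compliant woman, a missed capsule, poor absorption or fast metabolism. The June 2017 update considers only the preparation and fast metabolism.

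The second draw has a further problem. If it falls in the luteal phase, a level of 2-28 ng/ml may be the woman's own hormone, and a placebo participant can look exposed. The second cohort was opened because exposure was in doubt, so its levels need to be readable.

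The covariate analysis adds a third difficulty. The progesterone level is measured after randomisation and is affected by arm. Once it is in the model beside arm, the arm coefficient no longer estimates the randomised effect.

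**Working it through.** The plan states no figure to reproduce. Two checks use its own inputs.

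**1. Draw time within the dosing interval**

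Inputs from Treatment Conditions: peak at 2-3 h, half-life 3-4 h, twice-daily dosing. The 12 h spacing is an assumption.

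For a single dose, the fraction of peak left at time t is 2^(-(t - tmax)/t½). At t = 12 h:
- t½ = 3, tmax = 2: 2^(-10/3) = 0.099
- t½ = 3, tmax = 3: 2^(-9/3) = 0.125
- t½ = 4, tmax = 2: 2^(-10/4) = 0.177
- t½ = 4, tmax = 3: 2^(-9/4) = 0.210

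At 24 h, after one missed capsule, the same formula gives 0.006 to 0.026. One level therefore reflects roughly the last day of dosing.

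Repeated dosing raises the trough. A one-compartment steady-state model was used, with ke = ln 2/t½, and ka solved from ln(ka/ke)/(ka - ke) = tmax. Its peak-to-trough ratios, in the same order, are 7.7, 4.5, 4.9 and 3.5. That is about 3.5- to 8-fold.

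The documents give no peak concentration. For assumed peaks of 5, 10, 20 and 40 ng/ml, the single-dose 12 h values are 0.5-1.1, 1.0-2.1, 2.0-4.2 and 4.0-8.4 ng/ml. At the lower peaks a compliant trough comes close to the follicular background of under 1 ng/ml.

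**2. Cycle phase at each draw**

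Inputs: eligible cycle length L = 24-36 days (Inclusion criteria); Visit 2 on cycle day d = 7-11; weekly visits, so Visit 6 is 28 days and Visit 7 is 35 days after Visit 2. Assumptions: the luteal phase is the last 14 days of the cycle (12 as a sensitivity), and cycles do not change on treatment.

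Cycle day = ((d + offset - 1) mod L) + 1, luteal if above L - 14. With 13 lengths and 5 days there are 65 combinations, equally weighted.

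| Draw | Luteal, 14-day phase | Luteal, 12-day phase |
|---|---|---|
| Visit 2 | 1/65 | 0/65 |
| Visit 6 | 12/65 (18%) | 7/65 (11%) |
| Visit 7 | 26/65 (40%) | 21/65 (32%) |

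These are shares of a grid, not probabilities. With the 14-day phase:
- Visit 7 is luteal only in cycles under 30 days: 5, 5, 5, 5, 4 and 2 of the five days for L = 24 to 29, total 26.
- Visit 6 is luteal in 5, 3 and 1 of the days for L = 24, 25 and 26, and in 1 and 2 for L = 35 and 36, total 12.
- Both visits are luteal in 5 + 3 + 1 = 9 of 65, all in cycles of 24-26 days.

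The anchor matters. Counting 6 and 7 weeks from Visit 1 on cycle days 18-24 gives luteal shares of 51/91 (56%) and 41/91 (45%), and long cycles are then affected too. In the longest cycles that count cannot be squared with Visit 2 on days 7-11 (with L = 36, Visit 1 plus 14 days is day 32 at the earliest, or up to day 2 of the next cycle), so the Visit 2 anchor is used here.

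**3. Placebo comparison in the second cohort**

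With 12 women at 6:1, 12 × 6/7 = 10.3 and 12 × 1/7 = 1.7, so about 10 active and 2 placebo.

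**The case against.** The strongest reply is that the first draw already has a cycle anchor. It falls around days 7-11, follicular in 64 of 65 combinations, where the background is under 1 ng/ml. A clearly raised level there does show recent intake. In the first cohort, randomised 1:1, a comparison of arms can also show exposure at group level despite scattered draw times. A reader might infer that the levels cannot show exposure at all; the documents do not support that.

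A reader might also infer that draw timing or luteal hormone explains the June 2017 finding. The second draw was requested only in September 2017, so luteal confounding at that draw played no part. The finding concerned a whole arm, and timing alone would make an arm low only if draws clustered near trough. The documents do not say that they did, and do not describe the first cohort's draw times separately.

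Other points stand in part. Pill count is the named compliance measure. Cycle dating is done at baseline and a call confirms onset of menses, so some cycle information exists, but nothing shown links it to the second draw. The lab form is not among the documents and might record dose time. The 3.5- to 8-fold figure is the extreme contrast within an interval, not a typical difference. The covariate analysis is labelled exploratory and no primary test rests on it.

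What the reply does not answer is a low level at either draw, or a raised level at the second. With about 2 placebo women in the second cohort, a placebo comparison can hardly help.

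**Conclusion.** The point holds in a limited form. Without time since the last capsule, a low level at either draw cannot separate trough, missed dose, poor absorption and fast metabolism. Without cycle phase as well, a raised level at the second draw cannot separate drug from endogenous hormone. A clearly raised level at the first draw remains informative. No single level can confirm pill-taking over 8 weeks.

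The first part rests on the protocol's own kinetics and an assumed 12 h interval. The second rests on an assumed 14-day luteal phase, regular cycles on treatment and the Visit 2 anchor. The protocol lists menstrual irregularity as an adverse effect, which makes predicted cycle days less certain and recording them more useful. It would go too far to conclude that the June 2017 judgement was wrong or that the primary comparison is biased by these draws. The documents show only that draw timing and missed doses were not listed among the possible causes of the low levels.

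**What to change.** - Take each sample in a fixed window after a capsule, for example at the 2-3 h peak that the protocol quotes, by arranging the appointment around the capsule and leaving the dosing as it is.
- Record the time of the last capsule, the time of the draw and the cycle day for every sample.
- Take the second draw at whichever of Visit 6 or 7 is expected to be follicular. Where neither is (9 of 65 combinations, cycles of 24-26 days), do not read a raised level as exposure.
- State in the plan that the levels show recent intake, and that pill count is the measure of compliance over the trial.
- Report level against abstinence descriptively within the active arm. About 10 active women in the second cohort cannot support a model adjusted for several factors, and about 2 placebo women cannot supply a same-phase comparator.
- If a model contains both arm and the post-randomisation progesterone level, do not interpret its arm coefficient as the treatment effect.

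The cost is three fields on a form, a draw-time instruction and a few sentences in the analysis section. No extra blood is needed. The downside is less flexible appointments.

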Determination of Eligibility and Baseline Visit: This interview will occur between estimated days 18-24 of the typical menstrual cycle. This will be a 120 minute visit. It will be broken down into two parts: 1) we will determine eligibility for the randomized clinical trial (RCT) and 2) we will obtain baseline measures for those who are eligible. The first procedure will be obtaining informed consent (please see consent procedures below). In the process of consent, we will explain to the provisionally eligible participant that part of the visit will be to determine eligibility for the RCT. For determination of eligibility, women will complete the NIDA Quickscreen (10); DSM 5 psychosis screener and DSM 5 screener for major depressive disorder, panic disorder or post-traumatic stress disorder (PTSD; current). Any positive responses on these measures will trigger an evaluation, including the SCID and assessment by a study clinician (a physician for medical issues; a psychologist, physician or social worker if the issues is an exclusionary psychiatric diagnosis) that will indicate whether or not the participant is eligible; 2) a medical history will be gathered to obtain information on allergies, especially progesterone, use of medication, pregnancy planning, history of breast cancer, deep vein thrombosis, coagulation problems, liver failure, cervical intraepithelial neoplasm, allergy to nuts, etc; and 3) nicotine intake history including use of all nicotine products, number of cigarettes smoked and use of other nicotine products in the previous month, prior treatment for smoking cessation; prior intolerance or allergy to transdermal nicotine patch; 4) laboratory tests that include urine for pregnancy, cotinine and drugs of abuse and expired breath CO.

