The RA will complete a checklist that indicates eligibility criteria. The checklist will be reviewed by study clinician who will confirm that this information has been gathered and that the participant meets criteria for participation. For women who continue to be eligible, the RA and/or study clinician will ask baseline measures that include: 1) a menstrual history form including module for diagnosis of premenstrual dysphoric disorder and menstrual cycle dating, the Fagerstrom Test for Nicotine Dependence (FTND) (11); the Minnesotal Nicotine Withdrawal Scale (MNWS) (12), the Questionnaire on Smoking Urges-Brief (QSU-B) (13) and the Positive and Negative Affect Schedule(14) . They will also complete the following neurocognitive tasks: 1) the Stroop, (15) 2) Go/No Go, 3) Digit Symbol Substitution Test (part of the WAIS III), 4) The Shipley Institute of Living Scale (SILS) is a paper-and-pencil, self-administered scale that consists of a 40-item vocabulary and a 20-item pattern recognition section (16).

Randomization/Visit 1: After eligibility is confirmed and the baseline assessments are completed, women will be randomized. Women will then begin smoking cessation counseling and will receive two weeks supply of their study medication, TNP + either oral micronized progesterone or placebo. They will be instructed to apply one nicotine patch /day and to take one pill twice daily after the visit. They will be instructed to set a quit date for the 5 (+/-2) days after the onset of menses, ideally around the 3-4th day when perimenstrual symptoms have abated and before estrogen peaks. We will call them at the estimated time of menses onset to confirm dates and quit date plans. We used similar strategies in smoking studies and menstrual cycle studies (6).

Treatment Phase (Visit 2 to 8): Women will be seen for follow up around days 7-11 of their menstrual cycle, shortly after their quit date. This visit will confirm that treatment with TNP + progesterone or placebo was initiated and maintained for the estimated 2 weeks since Visit 1. Medication compliance will be assessed by pill count. Support and counseling will be

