Women who are provisionally eligible after screening will be seen for a confidential, in office assessment. We will have a checklist that study staff complete at the baseline assessment visit that lists eligibility/ineligibility criteria. The PI or PI-s designee must check the participant's document, verify the checklist and confirm eligibility according to inclusion and exclusion criteria.

9. **Risks:** Describe the reasonably foreseeable risks, including risks to subject privacy, discomforts, or inconveniences associated with subjects participating in the research.

Progesterone, a natural hormone, is safe and well-tolerated by women. The safety, tolerability and efficacy of micronized progesterone is well established and it is FDA approved for hormone replacement therapy (HRT), absence of menstrual periods (amenorrhea), endometriosis, infertility treatment and preterm delivery. The recommended dose of progesterone for hormone replacement treatment is 200 to 400 mg/day, given as a single evening dose. After oral administration, micronized progesterone reaches its peak plasma levels in two to three hours and has an elimination half-life of three to four hours (18). Because of its short half-life progesterone will be given twice daily to maintain stable plasma levels. Progesterone doses higher than 400 mg/day will not be used since they are more likely to cause sedation. The safety and tolerability of micronized progesterone are well established. We have used micronized progesterone in several previous studies with female smokers (4-6). Progesterone was well-tolerated and we did not encounter any serious adverse events. The most common adverse effect is mild sedation. Other less common adverse effects include menstrual irregularity, spotting or breakthrough bleeding, dizziness, cramps, nausea, fatigue, headache and breast tenderness. Other side effects attributed to synthetic progestins, including depression, fluid retention, pruritus, jaundice, rash and thrombotic disorders, have not been observed with natural progesterone. Women will be warned to use caution when driving a motor vehicle or operating machinery while undergoing study treatment.

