### **5. Plan for Determining Seriousness of Adverse Events:**

#### **Serious Adverse Events:**

In addition to grading the adverse event, the PI will determine whether the adverse event meets the criteria for a Serious Adverse Event (SAE). An adverse event is considered serious if it results in any of the following outcomes:

- 1. Death;
- 2. A life-threatening experience in-patient hospitalization or prolongation of existing hospitalization;
- 3. A persistent or significant disability or incapacity;
- 4. A congenital anomaly or birth defect; OR
- 5. Any other adverse event that, based upon appropriate medical judgment, may jeopardize the subject's health and may require medical or surgical intervention to prevent one of the other outcomes listed in this definition.

An adverse event may be graded as severe but still not meet the criteria for a Serious Adverse Event. Similarly, an adverse event may be graded as moderate but still meet the criteria for an

SAE. It is important for the PI to consider the grade of the event as well as its “seriousness” when determining whether reporting to the IRB is necessary.

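### The on-treatment pregnancy test is triggered by absence of recent menstruation, yet the study drug can itself cause bleeding, so a test can be suppressed or delayed

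*Combined protocol and SAP*

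**What the plan says.** **Before first dose.** The only unconditional pregnancy test is at the eligibility and baseline visit (Study Procedures, Determination of Eligibility and Baseline Visit): "laboratory tests that include urine for pregnancy, cotinine and drugs of abuse and expired breath CO". Its timing is given as "This interview will occur between estimated days 18-24 of the typical menstrual cycle". The Overview of the study design gives a second anchor: induction in the mid-luteal phase, no more than a week ahead of menses. Randomization and first dose follow directly (Randomization/Visit 1). Eligible cycles run from 24 to 36 days, and pregnancy is an exclusion (Section V, item 7).

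**During treatment.** Visit 2 is placed by cycle day: "Women will be seen for follow up around days 7-11 of their menstrual cycle, shortly after their quit date". The same paragraph also describes it as an estimated two weeks after Visit 1, at which two weeks of medication are dispensed. Staff telephone at the expected onset of menses. The test rule, under the weekly visits that follow, applies if pregnancy is possible: "i.e. she is not menstruating or in the week following menstruation) we will also test urine for positive pregnancy".

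**Drug effects on bleeding.** Section V, item 9 (Risks): "Other less common adverse effects include menstrual irregularity, spotting or breakthrough bleeding, dizziness, cramps". The Background paragraph on the safety of progesterone repeats this, and item 10 (Minimizing Risks) plans to monitor breakthrough bleeding.

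**After treatment.** For the 1- and 3-month visits: "At follow up, assessments of smoking and the PANAS will be repeated". The Moderate Risk DSMP, item 5, includes among its seriousness criteria "A congenital anomaly or birth defect".

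**The concern.** The rule treats recent menstruation as evidence that a woman is not pregnant. That inference weakens when the treatment can itself produce bleeding or disturb the cycle, and no section tells staff how to separate such bleeding from menses. A woman who conceived in the start cycle, tested negative at baseline and then bled on treatment could be exempted from testing while she continues blinded capsules and the nicotine patch, although pregnancy is an exclusion criterion. The baseline test is not a firm backstop, because it is taken in the luteal phase, possibly before a conception in that cycle would show.

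**Working it through.** **The plan's own figure: about two weeks from Visit 1 to Visit 2.** With cycle length C (24 to 36), Visit 1 on cycle day b (18 to 24) and Visit 2 on day v (7 to 11) of the next cycle, the interval is C − b + v. At the midpoints (b = 21, v = 9) this gives 26 − 21 + 9 = 14 days and 28 − 21 + 9 = 16 days. Under the Overview anchor, with Visit 1 falling d = 1 to 7 days before menses, the interval is d + v − 1, with midpoint 4 + 9 − 1 = 12. The stated two weeks reproduces as an approximation. Across all eligible cycles, however, the cycle-day anchor runs from 7 to 29 days, so the two ways of dating Visit 2 can diverge.

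**Timing of the baseline test and of later visits.** Assumptions: ovulation 14 days before menses; baseline and first dose on the same day; Visit 3 one week after Visit 2; bleeding taken for menses arrives when expected. Days after ovulation = b − (C − 14). Under the Overview anchor this is 7 to 13 or 8 to 14, depending on whether the day of onset is counted.

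| Anchor for Visit 1 | Test, days after ovulation | Days, Visit 1 to 2 | Days, Visit 1 to 3 |
|---|---|---|---|
| Overview, 1 to 7 days before menses, any cycle | about 7 to 14 | 7 to 17 | 14 to 24 |
| Days 18 to 24, 24-day cycle | 8 to 14 | 7 to 17 | 14 to 24 |
| Days 18 to 24, 28-day cycle | 4 to 10 | 11 to 21 | 18 to 28 |
| Days 18 to 24, 36-day cycle | −4 to 2 | 19 to 29 | 26 to 36 |

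If urine tests turn positive about 12 to 14 days after ovulation (an assumption; the documents give no figure), only the later end of the Overview window reaches that point.

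**Is Visit 2 exempt?** Read naturally, the rule exempts a woman who is menstruating or in the following week. The other parsing (not menstruating, or else in the following week) would make the second clause redundant, since a woman in that week is already not menstruating. For menses of M days the exemption covers cycle days 1 to M + 7:

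- M = 2: ends day 9, so days 10 and 11 are tested.
- M = 3: ends day 10, so day 11 is tested.
- M = 4: ends day 11, so no Visit 2 day is tested; the same holds for M = 5 to 7.

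Visit 3 falls on cycle days 14 to 18. That is outside the exemption for M = 4 to 6; with M = 7 (exempt through day 14) a Visit 3 on day 14 would still be missed.

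**Is testing lost altogether?** Non-exempt days per cycle are C − (M + 7): from 24 − 14 = 10 to 36 − 10 = 26, for M = 3 to 7. Even 10 days must contain a weekly visit, so with regular menses at least one visit per cycle is tested (two or three in a 28-day cycle). The exemption becomes continuous only if bleeding taken for menses recurs within about M + 7 days.

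**Last contact.** 8 weeks plus 3 months is 56 + 91 = 147 days, or 21 weeks from first dose. For a start-cycle conception, gestational age is then (147 + 24)/7 = 24.4 weeks with baseline on cycle day 24, and (147 + 36)/7 = 26.1 weeks with baseline at the end of a 36-day cycle. Both are below term (37 weeks or more, assumed).

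**The case against.** The harmful sequence is narrow. The woman must conceive despite required non-hormonal contraception, test negative at baseline, and then have bleeding mistaken for menses, which the protocol places among the less common effects. The documents give no probability for this chain and none is offered here. Breakthrough bleeding is monitored, and gynecological adverse events go at once to an independent gynecological consultant. That safeguard stands but does not close the gap: Strategies to protect the blind also has the consultant withhold these events from the rest of the team except when unblinding for safety, while saying they are reviewed at staff meetings. Staff applying the test rule may not know how a bleed was judged.

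Whether Visit 2 is skipped depends on the parsing and the assumed length of menses. Visit 2 also has its assessments repeated, which neither names nor rules out a urine test. This is accepted, and the ambiguity needs clearing in any case.

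A reader might infer that Visit 2 has no date when menses does not come, or that such a woman escapes testing. Neither is supported. Visit 2 has the two-week estimate, the two-week supply forces a return, and weekly meetings are stated under Strategies to protect the blind. A woman who has not bled also meets the test trigger. What is missing is which anchor governs.

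A reader might also see a contradiction between the birth-defect criterion and the length of follow-up. The DSMP item defines seriousness; it does not promise surveillance to term. This is an omission, and the removed consent pages may cover part of it.

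**Conclusion.** The concern holds for the trigger. Followed as written, the rule lets bleeding that the drug can cause stand as evidence against pregnancy, and the luteal-phase baseline test may be too early to exclude a start-cycle conception. On the natural reading, with menses of at least about 4 days, the first visit tested is about Visit 3. That is roughly 14 to 24 days after first dose under the Overview anchor, and up to 36 days if cycle days 18 to 24 are applied literally to a 36-day cycle. These figures rest on the assumed ovulation day and menses length; the view that baseline is early also rests on the assumed 12 to 14 days for a urine test to turn positive. The usual consequence is delay; the documents do not support a claim that testing is absent.

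Two lesser points remain. The two ways of dating Visit 2 are not reconciled for a woman whose menses does not come. And the supplied text does not say how a pregnancy found on study is handled or followed, although birth defect is a seriousness criterion and last contact is about 21 weeks after first dose.

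**What to change.** Reconcile the test trigger under Treatment Phase with the bleeding effects acknowledged in Background, Risks and Minimizing Risks, so that a pregnancy test does not depend on bleeding the drug can cause. State explicitly whether Visit 2 includes a test. Reconcile the two anchors for Visit 2 for a woman without menses, and the two anchors for the baseline visit (Overview versus Baseline Visit). Say how an on-study pregnancy is handled, reported and followed, and align this with the pregnancy exclusion and with the discontinuation and withdrawal provisions under Minimizing Risks, which do not mention a positive test.

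The testing schedule and the clinical rule are for the investigators to set. The cost is a few sentences, at most a few urine strips per woman at existing visits, and some follow-up contact if a pregnancy occurs.
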